Energy-Harvesting Knee Prosthesis:
Assist-Knee

NCT04023045
Protocol # 7826-01

Revised: 06/26/2019
Approved by IRB: 07/15/2019

Grant PI:
[name]

Orthocare Innovations, LLC
[name]
[name]

i. Purpose of the study and background

Geriatric individuals with transfemoral limb loss can find rising from a chair challenging due to a loss of knee and ankle musculature on the prosthetic side, and declining or marginal strength on the sound side. Transitioning from a sitting to a standing position is much more difficult for an individual with transfemoral limb loss than an individual with no limb loss. When rising from a chair, individuals with limb loss rely on their sound limb and upper limb strength to lift their body weight. Geriatric transfemoral prosthesis users could retain independence if a prosthetic knee was capable of assisting with sit-to-stand-to-sit transitions. Unfortunately, the current designs of non-powered prosthetic knees do not assist with the sit-to-stand-to-sit transition, a task that is fundamental for normal activities of daily living.

The objective of the *energy-harvesting knee prosthesis* (that we call **Assist-Knee**) is to create a lightweight, low-cost prosthesis that stores the prosthesis user's potential energy during the stand-to-sit (*SIT*) transition and appropriately returns that energy to assist with the sit-to-stand (*STAND*) transition. Assist-Knee combines a mechanical spring and damper with a safety interlock mechanism (**Figure 1**).

{ *figure redacted* }

Figure 1: CAD model of the Assist-Knee device

{ *text redacted* }

{*figure redacted*}

Figure 2: Assist-Knee function during **STAND** transitions. {*text redacted*}

{*text redacted*}

{*figure redacted*}

Figure 3: {*text redacted*}

{*text redacted*}

The purpose of the human subject testing will be to (1) validate the concept of the Assist-Knee design and function by testing the ability of Assist-Knee to harvest energy and return a sufficient amount of energy during the stand-to-sit-to-stand transition in a way that is clinically relevant, and (2) collect pilot data using the Assist-Knee device that can be included in a larger grant submission to perform a clinical trial with a larger representative population. We will also evaluate whether prosthetic users are able to wear and use the Assist-Knee device when walking.

ii. Criteria For Participant Selection

Our enrollment target for this pilot study will be 3 participants who are transfemoral prosthetic users. Our sampling plan for subjects will include both adult women and men (e.g. 1 adult woman and 2 adult men, or 2 adult women and 1 adult man). The target subject distribution represents the results of the United States Census 2010 for Seattle, Washington: Asian (8.6%), Black (4.1%), and Hispanic or Latino (12.4%). We will endeavor to recruit participants that match the local demographic distribution. However, researchers will consider persons of all racial and ethnic backgrounds as equal candidates for inclusion in this work. The work has the potential to benefit minorities and non-minorities equally.

The inclusion/exclusion criteria for the participants with lower limb loss are the following:

Inclusion Criteria

- Unilateral transfemoral limb loss
- Age 21 – 80 years
- At least one year post-amputation and currently successfully using a prosthesis
- Uses modular endoskeletal prosthetic components
- Has bilateral normal range of motion
- Ability to perform the following activities:
 - Walking ability or ability to take steps over 10 meters
 - Upright standing stability
 - Stand-to-sit stability (i.e. go from a standing position to a seated position independently)
 - Sit-to-stand stability (i.e. rise from a seated position independently)
- Ability to communicate individual perceptions in the English language
- Ability to provide informed consent

Exclusion Criteria

- Confounding injury or musculoskeletal problem
- Pregnancy
- Lower limb peripheral neuropathy
- Symptomatic cardiovascular disease or chronic obstructive pulmonary disease
- Not able to read and understand English
- Use of assistive devices for sit-to-stand and stand-to-sit (e.g. canes, walkers)

iii. Methods and Procedures

Recruitment of participants with lower limb loss

Recruitment will be by referral from collaborating prosthetists or Orthocare Innovations' study prosthetist. The prosthetist will either mail the attached letter (Assist-Knee solicitation letter.doc) or use the attached script (Assist-Knee solicitation script.doc) with patients that appear to meet the inclusion/exclusion criteria. If interested in participating in the study, the prosthesis users may choose to call Orthocare Innovations or choose to have Orthocare Innovations call them.

Once contact is made between the prosthesis user and Orthocare Innovations' research personnel, the Orthocare Innovations phone script will be followed (Assist-Knee solicitation script.doc). The research will be thoroughly described with opportunities for asking questions. Those interested in participating and those who meet our criteria will schedule an appointment for consenting at the Orthocare Innovations Biomechanics Laboratory. At this time, we will ask if they would like the consent document mailed or emailed to them so that they will have ample time to review the document prior to their visit. If they answer yes, we will mail or email a cover letter (Assist-Knee solicitation letter.doc) with a copy of the prosthesis user's consent document (Assist-Knee consent subject.doc).

Experimental procedures

Since each participant's prosthesis is unique, the prosthesis users will act as their own controls. All participants will have at least one visit to the Orthocare Innovations Biomechanics Laboratory, with each visit expected to last a minimum of four hours. The participants will first complete a baseline data collection using their existing habitual prosthesis. The participant's individual power harvesting performance, kinematic data, and kinetic data will be measured in the Orthocare Innovations Biomechanics Laboratory for baseline comparisons, using a motion capture system (Vicon, Centennial, CO and force plates (AMTI, Watertown, MA). The participants will be asked to perform a variety of common activity tasks that may include: sit-to-stand maneuvers, walking on level-ground; turns during walking on level ground; initiating gait from a standstill; and stand-to-sit maneuvers. The main focus of the data collection is during the sit-to-stand-to-sit maneuvers. The participants will also be asked to complete the Timed Up and Go (TUG) test, which requires the participant to stand up from a chair, walk 3 m, turn around, walk 3 m back to the chair, turn around, and sit down onto the chair. After baseline data have been collected, the prosthesis user will then wear Assist-Knee and complete the same data collection in the Biomechanics Laboratory. Subjects will be asked to complete the Prosthesis Evaluation Questionnaire (PEQ) and a custom survey after completing the data collection for each habitual or Assist-Knee condition (Assist-Knee_ParticipantQuestionnaire.docx). Subjects will also be asked to complete a demographic survey (Assist-Knee_Demographics.doc).

Participants will wear the Assist-Knee system (**Figure 4**), which is designed to fit in place of their existing knee prosthesis and ankle-foot prosthesis. {text redacted}

{figure redacted }

Figure 4: Representation of participant using Assist-Knee

An Orthocare Innovations study research prosthetist will fit each participant with the Assist-Knee device. The participant will be trained by the research prosthetist on how to use Assist-Knee with an acclimation period of at least 60 minutes, with rest periods as needed, or until the subject feels comfortable using the system independently for gait and sit-to-stand-to-sit transitions. We intend to provide ample training on the system before independent use and will provide an operator for the clinical study if necessary. We will then test the effect of Assist-Knee on various movements (sitting down, standing up, gait via TUG test) and collect kinetic, kinematic, and temporal-spatial data. The data will be collected using the Orthocare Innovations' Biomechanics Laboratory motion capture system (Vicon, Centennial, CO), force plates (AMTI, Watertown, MA), and a commercially available sensor (Smart Pyramid with Compas, Orthocare Innovations, Edmonds, WA) attached to the Assist-Knee.

To mimic current clinical practice, the Assist-Knee device will be aligned by the prosthetist in static alignment to an optimal state by consensus of the research prosthetist and participant. { text redacted } The subject will be given an acclimation period of at least 10 minutes, with rest periods as needed, or until the subject feels comfortable using the system with each new combination. When performing the activities during the entire experiment, the participant will wear a gait belt held by the clinician for safety. Kinematic and kinetic data will be recorded.

For each combination, subjects will perform a variety of tasks that may include: sit-to-stand maneuvers, walking on level-ground; turns during walking on level ground (e.g. for the TUG test); initiating gait from a standstill; and stand-to-sit maneuvers. The participants will not be allowed to use an assistive device during the sit-to-stand and stand-to-sit transitions, but the participants will be allowed to use an assistive device during the walking portion of the TUG test. The data

capture process is anticipated to take no more than three hours. An additional hour may be required to fit the prosthetic device and does not require active walking by the participant. Participants will be allowed to rest as needed. The collected data will be used to determine the effectiveness of the experimental device.

After testing { *text redacted* }, the participants will be encouraged to provide feedback on their perception of the device verbally and through the custom survey as well as complete the relevant questions from the PEQ.

The following table (**Table 1**) describes a representative order of events and the outcome measures collected. { *text redacted* }. At least five satisfactory trials of motion analysis data and at least three satisfactory trials of TUG test for each {*text redacted* } combination will be collected.

Table 1: Representative Experimental Protocol
Survey: Prostheses Evaluation Questionnaire (PEQ) and custom survey

Visit #	Activities to take place	Outcome Measures Collected
Hour 1	Screening, consent process, collection of demographic and anthropometric information, and administer survey for baseline prosthesis	Demographic and anthropometric information, baseline survey responses
Install Europa+ sensor in baseline prosthesis		
	Collect motion analysis data on a variety of tasks with baseline prosthesis, perform TUG test	Kinematic and kinetic data, TUG test
Training period with Assist-Knee { text redacted }		
	Collect motion analysis data on a variety of tasks with Assist-Knee prosthesis, perform TUG test, administer survey, open-ended discussion with prosthesis user	Survey responses, kinematic and kinetic data, TUG test, Assist-Knee settings
Acclimation period with Assist-Knee { text redacted }		
Hours 1-3	Collect motion analysis data on a variety of tasks with Assist-Knee prosthesis, perform TUG test, administer custom survey, open-ended discussion with prosthesis user	Survey responses, kinematic and kinetic data, TUG test, Assist-Knee settings
Acclimation period with Assist-Knee { text redacted }		
	Collect motion analysis data on a variety of tasks with Assist-Knee prosthesis, perform TUG test, administer custom survey, open-ended discussion with prosthesis user	Survey responses, kinematic and kinetic data, TUG test, Assist-Knee settings
Acclimation period with Assist-Knee		

	{ text redacted }	
	Collect motion analysis data on a variety of tasks with Assist-Knee prosthesis, perform TUG test, administer survey, open-ended discussion with prosthesis user	Survey responses, kinematic and kinetic data, TUG test, Assist-Knee settings
Return to baseline prosthesis		

iv. Data Analysis and Data Monitoring

Data collected for the subjects with limb loss will be: contact information, age, sex, race, ethnicity, anthropometric measurements (height, distance from distal end of socket to knee center and knee center to ground), body mass, description of current prosthesis, time since limb loss, and cause of limb loss (scientifically relevant). The outcome measures collected from the subject experiment include kinematic, kinetic, and temporal-spatial parameters of gait; various data from the sensor installed on the Assist-Knee device; a record of verbal feedback regarding perceptions of the device; and written feedback with the Prosthesis Evaluation Questionnaire (PEQ) and custom survey.

All subjects will be assigned a de-identified number that can be used to refer to subjects outside the research group, in order to protect confidentiality of the participant. Investigators solely participating in the human subjects experiments will only have access to subjects' first names. The research coordinator, study prosthodontist, and principal investigator will have access to first and last name, telephone number, email address, and mailing address. The research coordinator will use the mailing address (or email address) for mailing (or emailing) the consent prior to the first visit so the subject can review it at his/her leisure prior to the official consenting visit. All personal identifying information will be coded, keyed, and kept in locked file cabinets and/or on a password-protected computer.

v. Risk/Benefit Assessment

The risk to the participants will be minimal. The potential health risks to the participant with transfemoral limb loss are similar to those during routine prosthesis fittings. The difference is that the testing may go longer than the usual clinical visit. Therefore, fatigue from walking and performing the sit-to-stand-to-sit transitions more than usual is a risk. Subjects will be told that they can sit and rest at any time. There are no foreseen psychological, social, or legal risks for participants.

There is always a risk of privacy and confidentiality being breached. The privacy and confidentiality of subjects will be preserved using standard procedures for research data collection and storage. Uniquely identifying information will be coded and keyed. The key will be kept on a single password-protected computer

and destroyed at the termination of the study. Unique identifiers will not be included in study data files other than the coding key and the consent forms. All data will be maintained on secure password-protected computers and locked file cabinets. HIPAA regulations will be observed for any personal, identifiable health information collected from the subjects.

There are no direct medical benefits for participating in this study and, therefore, no alternative therapies or courses of action should the subject elect not to participate in this study. The primary benefit from participation is the advancement of prosthesis technology through the evaluation of our novel Assist-Knee device.

vi. Subject Identification, Recruitment, And Consent

Recruitment of individuals with limb loss will be by referral from collaborating prosthodontists or Orthocare Innovations' study prosthodontists. The prosthodontist will either mail the attached letter (Assist-Knee solicitation letter.doc) or use the attached script (Assist-Knee solicitation script.doc) with prosthesis users that appear to meet the inclusion/exclusion criteria. If interested in participating in the study, the prosthesis users may choose to call Orthocare Innovations or choose to have Orthocare Innovations call them.

Once contact is made between the prosthesis user and Orthocare Innovations research personnel, the Orthocare Innovations phone script will be followed (Assist-Knee solicitation script.doc). The research will be thoroughly described with opportunities to ask questions. Those interested in participating and those who meet our criteria will schedule an appointment for consenting at Orthocare Innovations' Biomechanics Laboratory. At this time, we will ask if they would like the consent document mailed or emailed to them so that they will have ample time to review the document prior to their visit. If they answer yes, we will mail or email a cover letter (Assist-Knee solicitation letter.doc) with a copy of the patient's consent document (Assist-Knee consent subject.doc).

Aside from the participant's time and transportation, there will be no cost to the participant. To compensate the participant's time and transportation costs, the prosthesis user subjects will be paid { *text redacted* } at the end of the study or at the time of withdrawal.

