## Statistical Analysis Plan

In this small pilot trial of three participants, we calculated and reported descriptive statistics (means and standard deviations) with the different conditions (Habitual and Assist-Knee) to determine ranges of values for the following measures:

- Time to complete sit-to-stand
- Time to complete stand-to-sit
- Timed Up and Go Test
- Percentage of Body Weight on Contralateral Side at 65 degrees knee flexion

Due to the small sample size, the use of parametric statistical analyses such as Analysis of Variance (ANOVA) and averaging as a single group are not appropriate. Instead, each participant served as their own control since each user's prosthesis is unique, and we analyzed these values and the extremes (e.g., how fast or slow the sit-to-stand or stand-to-sit times were), to better understand the effect of our investigational device and inform sample size calculations in future research.

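### Does the lack of a count of failed, repeated or assisted attempts make the planned Assist-Knee times misleading?

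*Protocol*

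**What the plan says.** Section iii of the protocol (Experimental procedures) sets a minimum amount of data for each combination: "At least five satisfactory trials of motion analysis data and at least three satisfactory trials of TUG test". The visible text does not say what makes a trial satisfactory, and part of that sentence is redacted. The same section states that "The collected data will be used to determine the effectiveness of the experimental device".

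Section iv lists what is gathered: "The outcome measures collected from the subject experiment include kinematic, kinetic, and temporal-spatial parameters of gait", followed by sensor data, a record of verbal feedback, the PEQ and a custom survey. Table 1 lists survey responses, kinematic and kinetic data, the TUG test and device settings. None of these entries is a tally of attempts or of help given.

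The SAP says "we calculated and reported descriptive statistics (means and standard deviations" by condition, Habitual and Assist-Knee. The measures are sit-to-stand time, stand-to-sit time, TUG time and one loading measure, "Percentage of Body Weight on Contralateral Side at 65 degrees knee flexion". It also says that the authors "analyzed these values and the extremes (e.g., how fast or slow the sit-to-stand or stand-to-sit times were", partly to "inform sample size calculations in future research".

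Section i gives the first aim as to "validate the concept of the Assist-Knee design and function". The same sentence then says how: by testing whether the knee stores energy and gives back enough of it during the transition.

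**The concern.** A time to complete a rise exists only if the rise is completed. An attempt that fails has no time, so it cannot enter the mean, the SD or the extremes of the times. If a satisfactory trial means a successful one, the failure is simply replaced. If it means a well-captured one, fewer times remain, and the SAP does not name the number of trials among its reported statistics. An attempt completed with support through the clinician-held gait belt keeps its time unmarked.

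For a device meant to help a user stand up, how often standing succeeds without help seems part of whether it works. A device that succeeded half the time could show the same times as one that always succeeded. A later trial with a success endpoint would then have no rate from this pilot to plan with.

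**Working it through.** The documents contain no sample size, power or event calculation to reproduce. The check is a reading of the outcome lists followed by an illustration.

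**1. Is a count planned anywhere visible?** Table 1, section iv and the SAP were read item by item. None contains attempts, failures, repeats or assistance. The factual premise holds, subject to redactions in section iii and Table 1 and to the custom survey not being supplied.

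**2. What does the trial requirement most naturally mean?** The wording attaches satisfactory to trials of motion analysis data, which points to capture quality (usable marker and force-plate data) rather than task success. It also sets a minimum, so it does not imply that collection stops at five. The sentence does not establish that failed rises are thrown away.

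**3. How large could the effect be?** Inputs: 5 motion trials and 3 TUG trials per combination (protocol, section iii). The success probability p is an assumption, as are independent attempts, exact stopping at the minimum, and treating the five motion trials as five rises.

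- If failures are replaced until r trials are obtained: expected attempts = r/p.
- Chance of at least one failure in r attempts, and so of one before the r-th success = 1 − p^r.
- If instead five attempts are captured whatever their outcome: expected completion times = 5p.

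| p (assumed) | 5/p | 1 − p^5 | 5p | 3/p | 1 − p^3 |
|---|---|---|---|---|---|
| 1.0 | 5.0 | 0% | 5.0 | 3.0 | 0% |
| 0.9 | 5.56 | 41% | 4.5 | 3.33 | 27% |
| 0.8 | 6.25 | 67% | 4.0 | 3.75 | 49% |
| 0.5 | 10.0 | 97% | 2.5 | 6.0 | 87.5% |

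These figures follow from the chosen p alone. The documents support no particular row. Section ii requires participants to rise and sit independently and excludes users of assistive devices for those transitions. Section iii provides at least 60 minutes of training and acclimation, or until the participant is comfortable using the system independently. These provisions make failure with the habitual prosthesis unlikely and failure with the new device less likely, though they do not rule it out.

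**4. What do the planned summaries still show?** Take five otherwise equal times, with one completed rise d seconds slower.

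- The mean moves by d/5 = 0.20d.
- The SD (divisor n − 1) becomes d√0.2 = 0.45d.
- The maximum moves by d.

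A struggling but completed rise is therefore visible, above all through the extremes that the SAP reports. A failed rise moves none of the times. The loading measure is different: it needs the knee to pass 65 degrees, not a finished rise, so an incomplete attempt could still contribute a value.

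**5. What would a count add?** Exact (Clopper-Pearson) 95% intervals within one combination:

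- 5 of 5: 48% to 100%
- 5 of 6: 36% to 100%
- 5 of 10: 19% to 81%

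Such a rate would describe what happened in the session. It would be too imprecise to plan a future trial on.

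**The case for a change.** The strongest case for acting is that the gap does not depend on how satisfactory is read: on either reading, a completion time comes only from a completed attempt. The protocol itself cares about unaided performance, because it bars assistive devices during the transitions. Yet a clinician holds a gait belt throughout and an operator may be provided, and no visible rule records when either helps. The gap may also be uneven, since the entry criteria cover the habitual prosthesis and not the new one, so uncounted failures would more likely fall under Assist-Knee. A walking aid is allowed in the walking part of the TUG, again with no visible rule to note its use. A log would be cheap.

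The first point stands: the three times are conditional on completion. The unevenness is a fair inference, but nothing in the documents shows that any attempt failed. The belt is described as a safety measure and the operator's role is not described, so treating either as help in completing a rise is conjecture. The walking-aid point matters only if a participant's aid use differs between the two conditions. The sentence on effectiveness is broad, but section i defines validation through energy storage and return, and completion frequency is not a stated objective. Motion recordings, sensor data and verbal feedback also give the investigators informal sight of attempts that went wrong.

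**Conclusion.** No change to the plan is needed. In the visible text no attempt count is planned, and the three times describe performance when the task is completed. Followed as written, however, the plan gives correct descriptive times and loads for three participants, each compared with themselves. It tests no hypothesis, and no stated rule or figure produces a wrong result. A completion rate would be an additional descriptive outcome beyond the stated aims, of unknown effect and very low precision.

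The undefined word is a gap that analysts fill sensibly: they screen trials for usable capture, give the number of trials behind each mean, and mention failed attempts if there were any. The SAP is written in the past tense, so a new per-attempt log may no longer be possible in any case.

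This conclusion rests on reading satisfactory as capture quality and on failures being uncommon given the entry criteria and training. Redacted text could bear on the first. If many rises had in fact failed, the times would need to be described as conditional on completion; that would be a matter for the report and not a defect in the plan.

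### The protocol text and Table 1 disagree on whether the habitual-prosthesis survey comes before or after baseline testing; if Table 1 is followed, the survey contrast is confounded with timing

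*Protocol*

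**What the plan says.** Protocol section iii, Experimental procedures, gives one rule for both devices: participants fill in the PEQ and "a custom survey after completing the data collection for each habitual or Assist-Knee condition".

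Table 1 defines its shorthand at the top: "Survey: Prostheses Evaluation Questionnaire (PEQ) and custom survey". Its first row, in Hour 1, reads "Screening, consent process, collection of demographic and anthropometric information, and administer survey for baseline prosthesis", and the outcome column of that row lists the baseline survey responses. Sensor installation follows. Only then comes the baseline testing row, "Collect motion analysis data on a variety of tasks with baseline prosthesis, perform TUG test", whose outcome column names kinematic and kinetic data and the TUG, with no survey.

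The first and last of the four Assist-Knee rows read "Collect motion analysis data on a variety of tasks with Assist-Knee prosthesis, perform TUG test, administer survey, open-ended discussion with prosthesis user". The two middle rows end "administer custom survey, open-ended discussion with prosthesis user".

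The text introducing the table says that it "describes a representative order of events and the outcome measures collected".

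Section iv of the protocol names the PEQ and custom survey among the collected outcome measures. The SAP lists four measures for descriptive reporting by condition: sit-to-stand time, stand-to-sit time, TUG, and percentage of body weight on the contralateral side. No survey is among them.

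**The concern.** The protocol gives staff two incompatible instructions for the same questionnaire. Under the text, both devices are rated after testing. Under the table, the habitual device is rated at rest, during screening and consent, and Assist-Knee is rated after testing.

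Participants serve as their own controls, so a difference in how the two conditions are surveyed passes directly into each person's contrast. Together with the verbal feedback, the surveys are the only evidence from the user's side. The protocol says the collected data will be used to determine the device's effectiveness, and section i says the pilot data may support a larger grant submission. An avoidable asymmetry in when the two ratings are taken would weaken any statement that users preferred one device.

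**Working it through.** The documents give no figure for this point, so the check compares the stated orders and then sets out what follows for the contrast.

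**Step 1. The two instructions side by side**

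| Survey | Experimental procedures text | Table 1 |
|---|---|---|
| Habitual | After habitual data collection | Hour 1 screening and consent row, before sensor installation and before baseline testing |
| Assist-Knee | After Assist-Knee data collection | After motion analysis and TUG, in all four rows |

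The two sources agree for Assist-Knee and conflict for the habitual prosthesis. The activity and outcome columns of Table 1 agree with each other: the survey appears in both columns of the Hour 1 row and in neither column of the baseline testing row. The entry is therefore not a stray phrase or a broken table cell. No redaction falls within the text sentence or within the activity wording of these rows.

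**Step 2. What precedes each survey if Table 1 is followed**

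- Habitual survey: no study tasks.
- First Assist-Knee survey: the whole baseline battery, then the training period (the protocol asks for at least 60 minutes of acclimation, or until the participant is comfortable), then Assist-Knee testing. The stated minimum per combination is five satisfactory motion-analysis trials and three satisfactory TUG trials.

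The protocol's own risk section names fatigue from the walking and the sit-to-stand-to-sit transitions.

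**Step 3. What this does to the within-person contrast**

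For one participant, let H(pre) and H(post) be the habitual score before and after baseline testing, and A(post) the Assist-Knee score after testing.

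- Text order: D(text) = A(post) − H(post)
- Table order: D(table) = A(post) − H(pre) = D(text) + [H(post) − H(pre)]

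The bracket is the timing term. Four things follow.

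1. Under the table order it enters every participant's contrast in the same form, so averaging or adding participants would not remove it.
2. It cannot be estimated, because the habitual survey is given only once. Its sign is unknown and it may be zero.
3. If staff followed the text for some participants and the table for others, the term would enter only some contrasts. With a target of three participants, one handled differently is 1/3 of the data.
4. D(text) is not a clean device effect either. It still carries the fixed habitual-first order and the gap in experience: at least one year since amputation and established prosthesis use, against a short acclimation on Assist-Knee.

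**The case against.** **The table is only representative.** This is true, and it means the order actually used is unknown. It does not reconcile the two places. The text states a rule for both conditions, and the sample schedule breaks it.

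**Rating a habitual prosthesis from everyday use is defensible.** This stands as a design argument. Participants are at least a year past amputation and already use a prosthesis successfully, although no minimum time on the current device is stated. But if this was the intention, the text would have to say so, and it says the opposite. It would also give the two ratings different reference frames, which is the difficulty.

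**Little hangs on it.** This largely stands. The available SAP text plans no survey comparison, the analysis is descriptive, and the aim is proof of concept. It limits the weight of the point, but the surveys remain a listed outcome.

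**The fix leaves larger differences in place.** This is correct for device order and unequal experience. It is no reason to keep a further difference that costs almost nothing to remove.

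Some stronger readings are tempting, and the documents do not support them.

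- A reader might infer that the survey comparison is biased, in all three participants. Bias is possible but not shown, and the statement about all three holds only if Table 1 was followed throughout.
- A reader might infer that the PEQ is missing for two of the four Assist-Knee blocks, because the middle rows name the custom survey alone. The text ties the surveys to each condition, and the SAP names two conditions, Habitual and Assist-Knee; the protocol calls the Assist-Knee blocks combinations. PEQ at baseline and at the first and last Assist-Knee blocks covers both conditions, and the table's legend suggests that the distinction is deliberate. The other sentence that might bear on this, about feedback after testing, is partly redacted and cannot carry the claim.
- A reader might want to change the questionnaire instructions so that participants rate only the tasks just done. The questionnaires are not among the documents, so that proposal has no basis here. Whether the SAP should cover the surveys is a separate question.

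**Conclusion.** The contradiction is real, and it concerns one item: when the habitual-prosthesis survey is given. If Table 1 is followed, habitual and Assist-Knee responses are taken at different points relative to testing, and the within-person survey contrast is confounded with timing and could be biased. This conclusion is conditional on Table 1 being the order in use, which the documents do not settle. Nothing in them allows the effect to be expressed in PEQ points or given a direction.

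The consequence is modest. None of the four SAP measures is touched. What is affected is any habitual versus Assist-Knee statement based on the PEQ or custom survey. The correction is worth making because it is more than clerical and costs almost nothing.

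**What to change.** In Table 1, take the baseline survey out of the Hour 1 screening and consent row and place it in the baseline motion-analysis and TUG row, listed after the tasks. Make the same move in the outcome column for the baseline survey responses. Table 1 then matches the Experimental procedures text and the timing already used for Assist-Knee.

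The SAP is written in the past tense, so the data may already be in hand. In that case, report which order was used for each participant and qualify any habitual versus Assist-Knee survey contrast accordingly.

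In either case, acknowledge that the fixed habitual-first order and the unequal experience with the two devices remain in the survey contrast.

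The cost is one table entry moved, with no added assessment. If data collection is complete, it is a sentence or two in the report.
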